#### 5.8.5 Visit 5 (Week $16 \pm 7$ days)

Subjects must be asked to abstain from vaginal intercourse in the 24 hours preceding Study Visit 5. The following will be performed, and research staff will record results in the source documents and CRF:

- 1. Changes in the following since last visit:
  - a. AEs
  - b. Concomitant medications
- 2. Pregnancy test (urine)
- 3. Self-collected vaginal swab for CT and GC NAATs
- 4. Targeted physical exam, as needed, based on symptoms
- 5. Subject diary review (sexual activity, product use since last visit)
- 6. Completed FSFI, SFQ, subject satisfaction with product, and subject sexual satisfaction questionnaires

7. Return of all unused study product and used applicators

#### 5.8.6 Post-intervention Follow-up Visit/Visit 6 (Week 20 ±7 days)

The following will be performed, and research staff will record results in the source documents and CRF:

- 1. Changes in the following since last visit:
  - a. AEs
  - b. Concomitant medications
- 2. Pregnancy test (urine)
- 3. Self-collected vaginal swab for CT and GC NAATs. This is not required for subjects who were withdrawn due to positive CT or GC NAAT
- 4. Targeted physical exam, as needed based on symptoms
- 5. Subject diary review (sexual activity since last visit)

#### 5.9 Unscheduled Visit(s)

The subject will be asked to return to the study site for evaluation if she develops symptoms or signs of illness and needs to be evaluated between scheduled visits. A targeted physical examination, as dictated by the symptoms, will be performed. Safety or other laboratory tests will be obtained as deemed necessary by the Investigator. Findings will be documented in the source documents and eCRF for unscheduled visits. AE assessment (including SAEs) will be recorded in the source documents and eCRF.

Subjects will be asked to contact the study site to obtain additional study product should their monthly supply be depleted in advance of their next scheduled visit.

#### 5.10 Early Termination

If a subject who has received study product withdraws or is withdrawn, an early termination visit will be conducted if the subject is willing. All activities listed for Visit 5 will be carried out unless medically contraindicated. CT and GC NAAT is not required at the Early Termination Visit if subject is being withdrawn due to positive GC or CT NAAT.

### 5.11 Clinical Laboratory Specimen Preparation, Handling and Storage

All laboratory specimens collected during study visits will be collected and processed by a trained study research team member, following site SOPs, MOPs, and all applicable site and local safety committee safety guidelines. All samples collected for uHCG will be tested onsite.

Vaginal swab specimens collected for NAATs will be processed, stored, and shipped to the central laboratory for testing as described in the MOP.

Returned applicators will be collected from subjects at each visit. Trained study staff will perform staining on used applicators onsite as described in the MOP.

### **6** Safety Reporting and Safety Monitoring

Since this clinical study is being conducted exclusively in the US, FDA regulations including safety monitoring and reporting responsibilities of Sponsor and Investigators must be followed to ensure the safety and protection of human subjects and accuracy of the data collected.

### 6.1 Responsibilities

Investigators participating in this clinical study are required to:

- Evaluate subject safety including assessment of AEs for seriousness, severity, and causality
- Notify the ICON GPHS Medical Monitor of SAEs within 24 hours of becoming aware of them
- Provide detailed written reports, including necessary documentation requested by the Sponsor or IRB, promptly following immediate initial reports
- Inform the IRB of AEs as required by applicable regulatory requirements

#### 6.2 Definitions

#### **Adverse Event (AE)**

Any untoward medical occurrence in a clinical investigation subject who has received a study product intervention and that does not necessarily have to have a causal relationship with the study product. An AE can, therefore, be any unfavorable and unintended sign (including an abnormal laboratory finding, for example), symptom, or disease temporally associated with the use of a study medicinal product, whether or not considered related to the study medicinal product.

#### **Serious Adverse Event (SAE)**

An SAE is any adverse event that results in any of the following outcomes:

- Death
- Life-threatening (immediate risk of death)
- Inpatient hospitalization or prolongation of existing hospitalization
- Persistent or significant disability or incapacity
- Congenital anomaly/birth defect

• Important medical events that may not result in death, be life-threatening, or require hospitalization may be considered an SAE when, based upon appropriate medical judgment, they may jeopardize the subject and may require medical or surgical intervention to prevent one of the outcomes listed in this definition

The term "life-threatening" in the definition of SAE refers to an event in which the subject was at risk of death at the time of the event. It does not refer to an event which hypothetically might have caused death if it were more severe.

The term "hospitalization" describes a period of at least 24 hours. Overnight stay for observation, treatment at an emergency room or treatment on an outpatient basis does not constitute a hospitalization. However, medical judgment must always be exercised and when in doubt the case should be considered serious.

#### **Non-serious Adverse Event**

A non-serious AE is any AE which does not fulfill the definition of an SAE.

#### **Treatment-emergent Adverse Event (TEAE)**

A TEAE is any AE occurring after the application of the study product and within the time of residual product effect, or pre-existing medical condition that worsens in intensity after the application of study product and within the time of residual product effect. The time of residual product effect is 7 days after the dose of the study product, when the effect of the product is still considered to be present based on change of vaginal pH from baseline.

#### **Unexpected Adverse Reaction**

An adverse reaction, the nature or severity of which is not consistent with the applicable product information (eg, Investigational New Drug (IND) Safety Data; see Investigator's Brochure).

### **6.3** Safety Reporting Requirements

#### **6.3.1** Reporting Interval

All AEs and SAEs will be collected and recorded following randomization.

The Investigators will follow all AEs that are deemed at least possibly related to investigational product and SAEs until resolution (return to pre-intervention status or stabilization of conditions deemed as chronic), even if this extends beyond the study-reporting period.

A subject will be considered as lost to follow-up if participation in AE assessment is not continued after:

- Three unsuccessful attempts at telephone contact (separated by at least 24 hours) following missed AE assessment visit or telephone consultation; followed by
- Issuance of a certified letter to last documented address of subject, and no response within 7 days of mailing

At any time after the completion of the study, if an Investigator becomes aware of an SAE that is suspected to be related to the investigational product, the Investigator will report the event to ICON GPHS within 24 hours of awareness. The Investigator will ensure that the appropriate IRB has been notified of the reported SAE in a timely manner per internal IRB reporting requirements.

#### **6.3.2** Notification of the Sponsor of Serious Adverse Events

Any AE that meets a protocol-defined serious criterion, must be submitted within 24 hours of site awareness.

The Medical Monitor will review and assess the SAE for regulatory reporting and potential impact on study subject safety and protocol conduct.

Other supporting documentation of the event requested by the Medical Monitor should be provided.

The Sponsor will be notified of any unexpected SAE with suspicion of being related to study drug. In addition, the Sponsor will be informed of any study procedure-related SAE which may warrant a change of any study procedure or halting of the study.

# 6.3.3 Regulatory Reporting for Studies Conducted Under Investigational New Drug Application

The Sponsor is responsible to report both serious and unexpected events that are associated with investigational product(s) to the FDA within the required timelines as specified in 21 CFR 312.32 (fatal and life-threatening events within 7 calendar days by phone or fax and all other SAEs in writing within 15 calendar days). All serious events designated as "not associated" to investigational product(s) will be reported to the FDA at least annually in a summary format.

### 6.4 Investigator's Assessment of Adverse Events

The determination of seriousness, severity, and causality will be made by a site Investigator.

#### **6.4.1** Assessment of Severity

Each AE will be assessed by the Investigator with regard to the following categories:

#### **Seriousness**

An SAE is defined as any untoward medical occurrence that at any dose:

- Results in death
- Is life-threatening; this means that the subject is at risk of death at the time of the event, and it does not mean that the event hypothetically might have caused death if it were more severe
- Requires inpatient hospitalization or prolongation of existing hospitalization
- Results in persistent or significant disability or incapacity
- Is a congenital anomaly or birth defect
- Is an important medical event that may not be immediately life-threatening or result in death or hospitalization but that may jeopardize the subject or require intervention to prevent one of the above outcomes; examples of such events are intensive treatment in an emergency room or at home for allergic bronchospasm, blood dyscrasias or convulsions that do not result in hospitalization, or development of drug dependency or drug abuse

Medical and scientific judgment should be exercised in deciding whether a case is serious and whether expedited reporting is appropriate.

#### **Intensity**

Investigators should assess the severity of AEs according to Common Terminology Criteria for Adverse Events (CTCAE) version 4.03. In general, CTCAE severity grades are:

- Grade 1: mild; asymptomatic or mild symptoms; clinical or diagnostic observations only; intervention not indicated
- Grade 2: moderate; minimal, local, or noninvasive intervention indicated; limiting ageappropriate instrumental activities of daily living (ADL) (instrumental ADL refer to preparing meals, shopping for groceries or clothes, using the telephone, managing money, etc)
- Grade 3: severe or medically significant but not immediately life-threatening; hospitalization or prolongation of hospitalization indicated; disabling; limiting self-care ADL (self-care ADL refer to bathing, dressing and undressing, feeding self, using the toilet, taking medications, and not bedridden)
- Grade 4: life-threatening consequences; urgent intervention indicated

#### • Grade 5: death related to AE

#### **Causality**

The Investigator will assess the causality/relationship between the study drug and the AE and record that assessment in the electronic data capture (EDC) system. The most likely cause of an AE (eg, concomitant disease, concomitant medication, other) will be indicated in the EDC system with details of the concomitant disease or medication or other cause.

The causal relationship of the AE to study drug will be described per World Health Organization (WHO) Uppsala Monitoring Centre (UMC) causality categories:

#### • Certain

- o Event or laboratory test abnormality, with plausible time relationship to drug intake
- Cannot be explained by disease or other drugs
- o Response to withdrawal plausible (pharmacologically, pathologically)
- Event definitive pharmacologically or phenomenologically (ie, an objective and specific medical disorder or a recognized pharmacological phenomenon)
- o Rechallenge satisfactory, if necessary

### • Probable/Likely:

- o Event or laboratory test abnormality, with reasonable time relationship to drug intake
- o Unlikely to be attributed to disease or other drugs
- o Response to withdrawal clinically reasonable
- o Rechallenge not required

#### • Possible:

- o Event or laboratory test abnormality, with plausible time relationship to drug intake
- o Could also be explained by disease or other drugs
- o Information on drug withdrawal may be lacking or unclear

#### Unlikely:

- Event or laboratory test abnormality, with a time to drug intake that makes a relationship improbable (but not impossible)
- o Disease or other drugs provide plausible explanations

### • Conditional/Unclassified:

- Event or laboratory test abnormality
- o More data for proper assessment needed, or
- Additional data under examination

- Unassessable/Unclassifiable:
  - o Report suggesting an adverse reaction
  - o Cannot be judged because information is insufficient or contradictory
  - o Data cannot be supplemented or verified

#### **6.4.2** Adverse Event Outcome Measures

The outcome of all AEs will be reported based on the following definitions, independent of whether they are serious or non-serious AEs, their severity, or their relationship to the investigational product:

- Recovered: fully recovered, or by medical or surgical treatment the condition has returned to the level observed at the first study-related activity after the subject signed the informed consent
- Recovering: the condition is improving and the subject is expected to recover from the event. This term should only be used when the subject has completed the study
- Recovered with sequelae: as a result of the AE, the subject suffered persistent and significant disability/incapacity (eg, became blind, deaf, paralyzed). Any AE recovered with sequelae should be rated as an SAE
- Not recovered
- Fatal
- Unknown: this term should only be used in cases where the subject is lost to follow-up

### 6.5 Study-related Adverse Events

See **Appendix A** for descriptions and grading criteria for anticipated study-related AEs. All AEs will be documented on the standard AE forms. AE forms for cutaneous AE grade 3 or higher will be sent to the Medical Monitor within 24 hours of awareness (non-serious or serious).

The reporting of an AE grade 3 or higher will prompt follow-up diagnostic work-up (eg, physical examinations, vital signs, descriptive assessment, subject diary, and clinical laboratory work). If the cutaneous AE is grade 3, subjects will be seen twice weekly until the severity is reduced to grade 2 or less at two consecutive follow-up visits (1 week) and not getting worse.

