### 17 Appendices

### Appendix A. Grading of Study-related Adverse Events

The table referenced below is a modification of the NCI Common Terminology Criteria for Adverse Events (v4.03, May 2009) tables, adjusted to display common AEs applicable to this study. A grading (severity) scale is provided for each AE term. A brief definition is provided to clarify the meaning of each AE term. Any clinical event deemed by the clinician to be serious or life threatening should be considered a Grade 4 event.

A semi-colon indicates 'or' within the description of the grade; a single dash (-) indicates a grade is not available. ADL = Activities of Daily Living.

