### **ESTIMATING SEVERITY GRADE**

For abnormalities NOT found elsewhere in the tables use the scale below to estimate grade of severity:

| GRADE 1 | Mild; asymptomatic or mild symptoms; clinical or diagnostic observations          |  |  |  |
|---------|---|--|--|--|
|         | only; intervention not indicated  |  |  |  |
| GRADE 2 | Moderate; minimal, local or noninvasive intervention indicated; limiting age-     |  |  |  |
|         | appropriate instrumental ADL*.  |  |  |  |
| GRADE 3 | Severe or medically significant but not immediately life-threatening;             |  |  |  |
|         | hospitalization or prolongation of hospitalization indicated; disabling; limiting |  |  |  |
|         | self-care ADL**.  |  |  |  |
| GRADE 4 | Life-threatening consequences; urgent intervention indicated.                     |  |  |  |
| GRADE 5 | (Death) is not appropriate for some AEs and therefore is not an option.           |  |  |  |

\*Instrumental ADL refer to preparing meals, shopping for groceries or clothes, using the telephone, managing money, etc.

\*\*Self-care ADL refer to bathing, dressing and undressing, feeding self, using the toilet, taking medications, and not bedridden.

[figure not shown]
| Adverse Event                    | GRADE 1          | GRADE 2           | GRADE 3              | GRADE 4           | GRADE 5 |
|----------------------------------|------------------|-------------------|----------------------|-------------------|---------|
| Vaginal inflammation             | Mild discomfort  | Moderate          | Severe discomfort    | Widespread areas  | Death   |
| Definition: A disorder           | or pain with     | discomfort or     | or pain and edema,   | of mucosal        |         |
| characterized by inflammation    | edema or redness | pain with edema,  | or redness; limiting | ulceration; life- |         |
| involving the vagina.            |                  | redness; limiting | self-care ADL;       | threatening       |         |
|                                  |                  | instrumental ADL  | small areas of       | consequences;     |         |
|                                  |                  |                   | mucosal ulceration   | urgent            |         |
|                                  |                  |                   |                      | intervention      |         |

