|                                  |                  |                   |                      | indicated         |         |
| Vaginal pain                     | Mild pain        | Moderate pain;    | Severe pain;         | -                 | -       |
| Definition: A disorder           |                  | limiting          | limiting self-care   |                   |         |
| characterized by a sensation of  |                  | instrumental ADL  | ADL                  |                   |         |
| marked discomfort in the vagina. |                  |                   |                      |                   |         |
| Vaginal burning                  | Mild burning     | Moderate          | Severe burning;      |                   |         |
| Definition: A disorder           |                  | burning; limiting | limiting self-care   |                   |         |
| characterized by a sensation of  |                  | instrumental ADL  | ADL                  |                   |         |
| marked burning in the vagina.    |                  |                   |                      |                   |         |
| Vaginal pruritus                 | Mild             | Intense;          | Intense; constant;   | -                 | -       |
| Definition: A disorder           |                  | intermittent;     | limiting self-care   |                   |         |
| characterized by an              |                  | limiting          | ADL or sleep; oral   |                   |         |
| uncomfortable feeling of itching |                  | instrumental ADL  | corticosteroid or    |                   |         |
| and burning in the vagina.       |                  |                   | immunosuppressive    |                   |         |
|                                  |                  |                   | therapy indicated    |                   |         |

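### Protocol Section 6.5 ties its 24-hour notice and its twice-weekly follow-up of severe AEs to 'cutaneous' events, an undefined word that does not literally cover the vaginal AEs graded in Appendix A

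*Protocol*

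**What the plan says.** Protocol Section 6.5 opens by sending the reader to Appendix A for the grading of the AEs expected in this study. It then sets three rules for severe events, and their scope differs:

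- Notice: "AE forms for cutaneous AE grade 3 or higher will be sent to the Medical Monitor within 24 hours of awareness (non-serious or serious".
- Work-up: "The reporting of an AE grade 3 or higher will prompt follow-up diagnostic work-up". This covers any AE of that grade.
- Follow-up: "If the cutaneous AE is grade 3, subjects will be seen twice weekly", until the event has settled to Grade 2 or less at two consecutive visits.

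Appendix A as available grades four terms: vaginal inflammation, pain, burning and pruritus. Each has its own Grade 3 definition. The entry for "Vaginal inflammation" counts small areas of "mucosal ulceration" at Grade 3; the entry for burning starts with "Severe burning".

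**The concern.** The product is a gel applied in the vagina, so the local reactions one would most want a medical monitor to hear about are vaginal. Appendix C warns subjects of burning or irritation there, and SAP Section 8.9.1 counts genitourinary events of FDA interest. The bracket at the end of the notice sentence shows that the sponsor wanted some severe events reported quickly even when they are not serious. Yet the word that sets the scope is an ordinary term for skin, while Appendix A describes Grade 3 ulceration as mucosal. A site that takes the word at face value would send no 24-hour form for a non-serious Grade 3 vaginal reaction; a site that reads it as any local reaction would. With up to 50 sites, practice could vary. What is at stake is the speed and consistency of medical oversight, not the efficacy analysis.

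**Working it through.** No arithmetic decides this point. The check is a reading of every direct-notice rule, every use of the scope word, and the grading table.

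**1. Which rules require direct notice to the Medical Monitor or the CRO?**

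| Protocol section | Event | Time limit | Reaches a non-serious AE? |
|---|---|---|---|
| 3.5 | Emergency unblinding | 24 hours | No |
| 6.1 and 6.3.2 | SAEs | 24 hours | No |
| 6.3.1 | Suspected related SAEs learned of after study completion | 24 hours | No |
| 6.5 | Cutaneous AEs of Grade 3 or higher | 24 hours | Yes |
| 6.6.2 | Pregnancy | 14 days | No |

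Section 6.5 is therefore the only rapid route for a non-serious AE. The table shows coverage; it does not measure importance.

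**2. Is the scope word defined?** It occurs twice, both times in Section 6.5 (the notice and follow-up sentences). It is not explained there, in the definitions of Section 6.2, in the abbreviations list or in the available part of Appendix A.

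**3. Does it name the graded events?** Of the four terms shown in Appendix A, none is called cutaneous.

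**4. Can a Grade 3 vaginal AE be non-serious?** Yes. The general Grade 3 wording in Section 6.4.1 mentions hospitalization and disability, which overlap the SAE criteria. In Appendix A that general scale is reserved: "For abnormalities NOT found elsewhere in the tables use the scale below to estimate grade of severity". None of the four vaginal Grade 3 definitions mentions hospitalization, disability or threat to life. Appendix A also says "A semi-colon indicates 'or' within the description of the grade", so small areas of ulceration alone are enough for Grade 3. An investigator could still judge such a case serious, but the grade does not make it so.

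**5. What does a non-serious Grade 3 vaginal AE get if the word is read literally?**

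- Diagnostic work-up at the site (Section 6.5): yes.
- Entry in the electronic data capture system within 72 hours of study activity (Sections 9 and 9.1): yes.
- Follow-up until recovery if possibly or probably related (Section 6.6.1): yes.
- 24-hour form to the Medical Monitor: not required.
- Twice-weekly visits: not required.

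**6. Timing.** If the site learns of the event at a visit, both clocks start together and data entry may come up to 72 − 24 = 48 hours after the notice would have been due. If awareness and visit differ, this subtraction does not apply. In either case, data entry is not addressed to the Medical Monitor.

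**The case against.** The best defence is context. Section 6.5 concerns study-related AEs and starts from Appendix A, where every term shown is vaginal. On a literal reading the notice rule would miss the very events the section was written for, so the natural inference is that the word was used loosely for local application-site reactions. That is probably right. It makes this a matter of wording, but it does not make the wording safe: the same paragraph sets any AE of Grade 3 or higher (work-up) against cutaneous ones (notice and visits), and a careful site could take the contrast as deliberate.

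Second, part of the text is unavailable. The table of contents lists an Appendix B on study-related AEs, which does not appear under its own heading in the available text, and the Manual of Procedures is a separate document. Either might settle the scope. This limit stands, and no fault is implied by the absence.

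Third, the gap is narrow. Serious events go in within 24 hours whatever their grade, important medical events can be judged serious, and Section 6.2 says doubtful cases are to be treated as serious. Subjects are told to stop use and consult the site (Appendix C), symptoms lead to an unscheduled visit (Section 5.9), and intervention-related toxicity leads to discontinuation (Section 3.6.1). All of this stands, and it is why the point is minor. These safeguards act at the site or through the SAE route; none requires prompt notice to the Medical Monitor of a non-serious event.

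Finally, nothing in the protocol says that non-serious Grade 3 vaginal AEs must reach the Medical Monitor in 24 hours, so no stated requirement is contradicted. That is also correct. The case rests on the evident purpose of the rule.

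**Conclusion.** The point holds as a minor, inexpensive improvement to safety oversight. Taken literally, Section 6.5 gives no 24-hour Medical Monitor notice, and no twice-weekly follow-up, for a non-serious Grade 3 reaction at the product's own application site.

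A reader might infer more: that severe vaginal reactions would go unrecorded or unmanaged, that the sponsor chose to leave them out, or that the safety results would be distorted. The documents support none of these. Such events are worked up, entered and followed; the likely intent was to include them; and SAP Section 8.9.1 summarises and lists all AEs regardless of how fast the Medical Monitor heard of them.

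The documents give no rate for these events, so the number of women affected cannot be estimated; it is probably small. Efficacy results and type I error are not touched. The conclusion assumes that neither Appendix B nor the Manual of Procedures defines the word. If either does so to include vaginal reactions, only a cross-reference is needed.

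**What to change.** In the notice sentence of Section 6.5, replace the single word cutaneous with *vaginal, other genital, or cutaneous*. In the same clarification, state whether the twice-weekly follow-up sentence has the same scope. Changing the notice sentence alone would leave the two sentences at odds and invite a narrow reading of the follow-up rule. The cleaner solution is one defined term, such as *local (vaginal, other genital, or cutaneous) AE*, used in both places.

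The cost is a short protocol clarification and a memo to sites, a few more 24-hour forms and, if the follow-up scope is aligned, a few extra visits for rare Grade 3 local reactions.
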